8.1.2. Oral Mucocutaneous Lesions

Aphthous ulcers were observed in 5 of 66 (7.5%) of healthy volunteers randomized to ALPN-101 in the previous study in healthy volunteers. All events were mild or moderate and were self-limited or resolved with topical therapy (i.e., lidocaine; corticosteroids).

Oral mucocutaneous lesions (including aphthous ulcers) not attributed to SLE are considered AEIs for assessment in the present study; any oral mucocutaneous lesions attributed to underlying SLE should be reported in the appropriate disease index and not as AEs. Guidelines for reporting oral mucocutaneous lesions are provided in §9.8 and §9.8.2.

The differential diagnosis of new or worsening oral mucocutaneous lesions that may occur during this study includes, but is not limited to: new or worsening SLE activity; infections (e.g., coxsackie A, herpes simplex, herpes zoster, cytomegalovirus, Epstein-Barr, HIV, TB; other bacterial or fungal infections); trauma (e.g., dental appliances); drug reactions (e.g., methotrexate-related mucositis, others); other autoimmune or inflammatory diseases (e.g., inflammatory bowel disease; Behcet's; others). If new oral mucocutaneous lesions are observed during this study, efforts should be made to definitively determine cause, to the extent possible.

Evaluation should include:

• Culture to assess for infection, if indicated

• Consider specialist evaluation by ear, nose and throat or oral medicine if diagnosis is not clear; biopsy may be indicated in severe or refractory cases

• For lesions reported as AEIs: photographic documentation of lesions at presentation and in the event of significant change

Therapy should be guided by diagnosis, severity, and response to initial therapy. Options may include:

- Oral and/or topical analgesics, if indicated for discomfort
- Topical corticosteroids, if indicated for control of inflammation
- Treatment of underlying condition

8.1.3. Infections Grade ≥ 3

In general, study drug administration should be withheld in the event of any infection that the Investigator judges to be clinically significant. If the infection resolves, study drug may be restarted at the next scheduled dose, with approval of the Medical Monitor. For this study, infections of Grade ≥ 3 are considered AEIs (see §9.8.3). Reporting requirements for AEIs are described in §9.8.

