8.2. Allowed Medications or Treatments

8.2.1. Non-SLE Concomitant Medications

Use of non-SLE concomitant medications (including prescription and over-the-counter medications, herbal supplements/teas and vitamins, analgesics, non-prescription NSAIDs and other agents for treatment of AEs or supportive care that are not specifically prohibited) is permitted when deemed necessary by the Investigator or subject's care provider; subjects who are using NSAIDs infrequently or "as needed" should make every attempt to withhold dosing on study visit days until SLE assessments have been completed.

For all non-SLE concomitant medications used at baseline, or that are used intermittently and expected to be used during the study (e.g., NSAIDs for menstrual discomfort; rescue inhalers for asthma), name and indication should be recorded in the medical history.

For all non-SLE medications initiated during the study, date of initiation, dose, date of change in dose or discontinuation, and indication should be recorded. The associated AE should be documented.

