6.21. Restricted/Rescue Medications

During the Treatment Period, subjects treated with new concomitant medications or increased dose of the existing treatment will be considered non-responders (treatment failures) for assessments of SRI-X, BICLA, SLEDAI-2K Improvement, and 50% Improvement in CLASI activity score efficacy endpoints for visits after taking the restricted medication. Criteria for restricted/rescue medications include the following:

- Oral corticosteroids (prednisone, methylprednisolone, prednisolone, fludrocortisone acetate) can be taken during the study per the protocol criteria however the following would qualify the subject as a treatment failure:
 - Increase in dose from baseline of oral corticosteroids (burst) from Day 1 through Day 141 lasting more than 14 days (i.e., subject must taper back down to baseline dose level by Day 14 of the increase; for subjects not previously taking oral corticosteroids, taper must be down to 0 mg/day within 14 days); such a course also cannot be initiated more frequently than every 28 days
 - Dose greater than 40 mg prednisone/day (or equivalent)
 - Initiation of new oral corticosteroids or an increase in dose after Day 141
- Intramuscular corticosteroids can be taken during the study however, the following would qualify the subject as a treatment failure:
 - Intramuscular methylprednisolone dose greater than 160 mg administered at a single timepoint from Day 1 through Day 169
 - Intramuscular corticosteroids given at a frequency greater than 28 days
 - Initiation of new intramuscular corticosteroids or an increase in dose after Day 141

- Topical corticosteroids can be taken during the study however, the following would qualify the subject as a treatment failure
 - Increase in dose from baseline of topical corticosteroids (burst) from Day 1 through Day 141 lasting more than 14 days (i.e., subject must taper back down to baseline dose level by Day 14 of the increase; for subjects not previously taking topical corticosteroids, taper must be down to 0 mg/day within 14 days); such a course also cannot be initiated more frequently than every 28 days
 - Initiation of new topical corticosteroids or an increase in dose after Day 141
- Intravenous corticosteroids
- Increase in dose or addition of hydroxychloroquine or hydroxychloroquine-like drugs (hydroxychloroquine, hydroxychloroquine sulfate, chloroquine phosphate)

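### SAP 6.21 applies its topical-corticosteroid limits whatever the indication, so a late, long or quickly repeated course for a non-SLE oral lesion counts as non-response on SRI-4 and BICLA

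*SAP*

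**What the plan says.** SAP 6.21 introduces the topical rules with permission: "Topical corticosteroids can be taken during the study however, the following would qualify the subject as a treatment failure". It then gives three triggers:

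- A long course: "Increase in dose from baseline of topical corticosteroids (burst) from Day 1 through Day 141 lasting more than 14 days". A subject using no topical steroid at baseline must be back to none within the same two weeks.
- A limit on repetition: "such a course also cannot be initiated more frequently than every 28 days".
- A separate rule for late use: "Initiation of new topical corticosteroids or an increase in dose after Day 141".

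No indication, body site or adverse-event exception is attached to any of them. A later bullet in the same section, on newly started drugs, is limited to drugs given to treat SLE.

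Subjects who meet a trigger "will be considered non-responders (treatment failures) for assessments of SRI-X, BICLA" and for the SLEDAI-2K improvement and CLASI endpoints, at visits after the medication. SAP 7.4.2 treats restricted medication as intercurrent event IE2. IE2 means non-response for the binary primary and secondary endpoints, and exclusion of later SLEDAI-2K values from the MMRM. SAP Table 2 repeats the non-responder rule for SRI-4, BICLA, LLDAS and the CLASI endpoint.

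Protocol 8.1.2 makes oral mucocutaneous lesions not attributed to SLE adverse events of interest (AEIs). Its treatment options for oral lesions include "Topical corticosteroids, if indicated for control of inflammation". It also reports: "Aphthous ulcers were observed in 5 of 66 (7.5%) of healthy volunteers randomized to ALPN-101". Protocol 8.2.1 permits "other agents for treatment of AEs or supportive care that are not specifically prohibited". The steroid burst limits in Protocol 8.2.2.3 cover oral and intramuscular routes only, so the topical limits appear only in the SAP.

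**The concern.** The primary efficacy endpoints are meant to measure lupus activity. A topical steroid given for an ulcer that the investigator does not attribute to lupus says nothing about lupus control. Under the literal rule it can still decide the subject's result.

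The event that leads to the topical steroid may also depend on treatment. Protocol 2.7 lists aphthous ulcers among the most common adverse events in healthy volunteers on ALPN-101. If they are more frequent on ALPN-101 than on placebo in this trial, the rule removes more responders from the active arm, and part of a tolerability signal is counted as lack of efficacy.

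No protocol text overrides this reading, because Protocol 10.1 and 10.5.4 give the SAP precedence. SAP 8 meanwhile describes its analyses as consistent with the protocol.

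**Working it through.** **1. Following the rules for one subject.** Take a subject who meets every SRI-4 component at Day 169.

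- *Aphthous ulcer not attributed to SLE, topical steroid started on Day 150.* Protocol 8.1.2 lists the treatment as an option and 8.2.1 permits it. SAP 6.21 scores a start after Day 141 as failure, and SAP 7.4.2 makes the subject a non-responder.
- *Same ulcer on Day 60, one 10-day course.* No trigger is met, and the subject remains a responder.

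The two subjects have the same lupus outcome and the same indication. Only the timing differs.

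**2. The plan's own power figures.** SAP 4.2 uses 65 per arm, two-sided alpha 0.05 and a chi-square test. With the pooled-variance normal approximation, power = Φ[(Δ − 1.96·SE0)/SE1].

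- SRI-4, 40% vs 65%: SE0 = √(2·0.525·0.475/65) = 0.0876; SE1 = √((0.24 + 0.2275)/65) = 0.0848. Power = Φ(0.923) = 82.2% (stated 82%).
- BICLA, 20% vs 45%: SE0 = 0.0822, SE1 = 0.0792. Power = Φ(1.124) = 86.9% (stated 87%).

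The SAP reports that enrolment stopped at 76, taken here as 38 per arm. The same formula then gives 59.1% and 64.8%.

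**3. Ulcer rate.** 5/66 = 7.58% (the protocol prints 7.5%); exact 95% CI 2.5% to 16.8%. At 38 per arm this is 38 × 0.0758 = 2.9 subjects on ALPN-101.

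**4. Effect on the treatment difference.** Let q = ulcer rate × share of ulcer subjects whose topical course meets a trigger. The ALPN-101 response becomes p(1 − q). The placebo rate is left alone, which assumes no such failures on placebo. The documents do not give the share. The value 1/6 assumes that onset is uniform over 168 days, that every ulcer gets a topical steroid, and that only starts in the last 28 days count (28/168).

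| Ulcer rate | Share | q | Subjects of 38 | SRI-4 difference | SRI-4 power, 65/arm | SRI-4 power, 38/arm | BICLA power, 38/arm |
|---|---|---|---|---|---|---|---|
| 5/66 | 0 | 0 | 0 | 25.0 | 82.2% | 59.1% | 64.8% |
| 5/66 | 1/6 | 1.3% | 0.48 | 24.2 | 79.5% | 56.1% | 62.9% |
| 5/66 | 1/2 | 3.8% | 1.44 | 22.5 | 73.5% | 50.2% | 59.1% |
| 5/66 | 1 | 7.6% | 2.88 | 20.1 | 63.2% | 41.5% | 53.2% |
| 16.8% | 1/6 | 2.8% | 1.06 | 23.2 | 75.9% | 52.5% | 60.6% |

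In the 1/6 row, 0.48 × 0.65 = 0.31 responder is lost, and 0.31/38 = 0.8 point. One whole reclassified responder costs 1/38 = 2.6 points; two cost 5.3.

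**5. If placebo subjects have the same lesion rate.** Both response rates are multiplied by (1 − q), so the difference becomes 25 × (1 − q): 24.7 points at q = 1.3% and 23.1 at q = 7.6%. The dilution is then smaller and no longer specific to one arm.

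**The case against.** The strongest defence is that ignoring the indication is a legitimate composite estimand. A topical steroid can act on items that are scored: SLEDAI-2K rash and mucosal ulcers (2 points each), the CLASI mucous membrane item and the BILAG mucocutaneous domain. Protocol 8.1.2 concedes that the cause of an oral lesion may be unclear. A rule that ignores the investigator's label avoids attribution calls close to Day 169. This has some force and is the reason to keep the present rule as a sensitivity analysis. It does not justify the rule as the main analysis, because lesions not attributed to SLE are not meant to be scored as lupus activity at all.

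A second defence is that the section concerns rescue and uses the word burst, which Protocol 8.2.2.3 ties to increased SLE activity. That makes the 14-day rule arguably ambiguous. It does not help the post-Day 141 rule, which mentions neither a burst nor SLE.

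Third, the oral, intramuscular and intravenous bullets also name no indication, and Protocol Table 3 mentions corticosteroids for infusion reactions. That is correct. The oral and intramuscular limits do, however, have a counterpart in Protocol 8.2.2.3, and the topical limits have none. This point is confined to topical use.

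A reader might infer that any new topical steroid is a failure. It is not: a course up to Day 141 that lasts 14 days or less and is not repeated within 28 days is allowed. A reader might also infer that bias against ALPN-101 is established. The documents give no placebo ulcer rate, and Protocol 8.1.2 lists causes that can arise in either arm, such as infection, trauma and methotrexate mucositis.

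**Conclusion.** The point holds in this form. The topical triggers apply whatever the indication, so a topical course for a non-SLE condition that is started or increased after Day 141, runs beyond 14 days or is repeated within 28 days makes the subject a non-responder for SRI-4, BICLA, LLDAS and the CLASI endpoint. It also removes later SLEDAI-2K data from the MMRM. SAP 6.21 itself does not list LLDAS; that consequence comes from SAP 7.4.2 and Table 2.

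The likely size is small. At the 5/66 rate with late starts only, it is about half a subject in 38 and 0.8 point of a planned 25-point difference. The loss of 4.9 points, when every ulcer subject meets a trigger, is the ceiling at that rate. A loss of 2.6 to 5.3 points requires one or two actual responders to be reclassified and should be read as illustration only.

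The direction is against ALPN-101 only if such lesions are more frequent on it. The figures rest on 38 per arm, the healthy-volunteer rate carried over to SLE, ulcers independent of response, and an unknown share treated with topical steroid. Protocol 4.4.4 says that no earlier trial dosed beyond 4 weeks, so the 24-week rate is unknown.

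These are the SAP's primary efficacy endpoints. The trial's primary objective is safety, and the sample size was not set for formal efficacy testing, which limits the weight of the point but does not remove it.

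**What to change.** Before unblinding, amend SAP 6.21 to reconcile it with Protocol 8.1.2 and 8.2.1. Topical corticosteroid use should count as IE2 only when its recorded indication is SLE activity. Use for an adverse event or another non-SLE condition, including oral lesions reported as AEIs, should not count. Ambiguous indications should be classified by blinded review. Keep the present indication-blind rule as a sensitivity analysis for SRI-4 and BICLA.

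The data already exist. Protocol 8.2.1 has the indication and associated adverse event recorded for non-SLE drugs started on study, and Protocol 9.8.2 has SLE activity entered as the indication when an oral lesion is attributed to lupus. The cost is a sentence or two in the SAP, a filter on concomitant-medication records and review of probably few cases. The downside is some reliance on investigator attribution, which the sensitivity analysis makes visible. Only the analysis classification changes; clinical management does not.

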7. STATISTICAL METHODS AND ANALYSIS

Summaries of study data will be presented by treatment group (ALPN-101 or placebo) and for all subjects combined, as applicable.

Summaries of continuous data will present the number of non-missing observations (n), mean, standard deviation (SD), median, minimum (min), and maximum (max). Min and max values will be reported using the same number of decimal places as the raw data values; mean and medians will be reported to one more decimal place than the raw data values; and SD will be reported to two more decimal places than the respective raw data. If the raw data have three decimal places or more, three decimal places will be presented for all statistics.

For categorical data, the frequency in each category and the percentage of the relevant population will be presented. In general, percentages will be presented to one decimal place. Percentages equal to 100 will be presented as 100% and percentages equal to 0 will be presented as 0%.

Analyses will be conducted using SAS®, version 9.4 or higher.

7.1. Subject Accountability and Disposition

Subject disposition will be summarized by treatment group and for all subjects combined. The summary of subject disposition will include the numbers of subjects screened and randomized, the number of randomized subjects in each randomization stratification category, the number of subjects treated, and the numbers of subjects in each analysis population. The number and percentage of subjects in the randomized population who completed study treatment and who discontinued study treatment prematurely will be summarized with the primary reasons for treatment discontinuation. Similarly, the number percentage of subjects in the randomized population who completed the study and who permanently discontinued from study participation prematurely will be summarized with the primary reasons for study discontinuation.

A summary of the number and percentage of subjects screened, randomized, and completing study participation will be presented by geographic region and country within geographic region.

A listing of disposition for all randomized subjects including date of the subject's completion or discontinuation and reasons for treatment or study discontinuation will be presented. A separate listing of analysis populations and randomization stratification will also be provided.

Protocol deviations will be tracked throughout the study. Deviations may be related to inclusion/exclusion criteria, trial conduct, subject management or subject assessment. Prior to database lock all deviations will be reviewed and designated as important or not important. A summary of the number and percentage of subjects in the randomized population with important protocol deviations reported will be presented by treatment group and type of deviation. A bysubject listing of important protocol deviations will be provided.

7.2. Demographics and Baseline Characteristics and Medications

Descriptive summaries of demographics and baseline characteristics will be presented by treatment group for all randomized subjects. No formal statistical comparisons between the treatment arms will be performed. A by-subject listing of demographic and key baseline data will be provided.

History of significant non-SLE conditions and current medical conditions reported at screening and/or baseline will be summarized by Medical Dictionary for Regulatory Activities (MedDRA) system organ class (SOC) and preferred term (PT). The number and percentage of subjects in each treatment group of the safety population who reported each SOC and PT will be reported.

The number and percentage of unique subjects in the safety population who report use of prior and concomitant medications will be summarized separately by treatment group and for all subjects combined. Prior medications are medications with start and end dates prior to the date of the first dose of study drug. A medication that was started prior to the first dose of study drug and continued after first dose of study or that has a first dose date after the first dose of study drug will be summarized as a concomitant medication. An additional table summarizing all concomitant medications which are initiated on or after the date of the first administration of study drug will be provided. Concomitant medications for treatment of SLE, including concomitant corticosteroids, will be summarized separately. A single subject will be counted once, regardless of the number of times a specific medication was used.

Oral corticosteroid use during the study will be summarized for the mITT population using the following variables:

- Incidence of subjects oral corticosteroid use
- Incidence of subjects with changes in oral corticosteroid use
- Total exposure to oral corticosteroid use (area under the oral corticosteroid exposure curve while on study treatment) using prednisone-equivalent doses as described in Appendix 15.6
- Duration (days) of oral corticosteroid use while on study treatment

Rescue medications will be summarized for the mITT population for each treatment group and for all subjects combined.

A listing of all reported medications will be presented that includes the verbatim medication name reported, the Anatomical Therapeutic Chemical (ATC) coded terms, dosage, and frequency. Additionally, a listing of restricted medications taken during the study will be presented.

7.3. Treatment Exposure and Compliance

The extent of exposure to study drug will be summarized for the safety population by treatment group. Exposure duration in days will be calculated as defined in Section 6.2. Descriptive summaries of exposure days and the number and percentage of subjects in each exposure duration category, defined as ≥ 4 weeks, ≥ 12 weeks and ≥ 24 weeks will be presented.

To assess compliance with protocol-specified administration of study treatment, subjects in the safety population who missed a study drug infusion at any scheduled dosing visit prior to treatment completion or discontinuation or who do not receive the targeted amount of study drug are considered non-compliant. The number and percentage of non-compliant subjects will be summarized by treatment group and visit.

Overall compliance will be summarized descriptively. A by-subject listing of study drug administration will be provided.

7.4. Analysis of Efficacy Endpoints

7.4.1. General Considerations

Unless otherwise stated, all efficacy analyses will be conducted on the mITT population according to the randomized treatment. For efficacy endpoints, point estimates of treatment differences and 95% confidence intervals (CI) will be provided. Two-sided p-values will also be provided for efficacy endpoints, as applicable. Where possible, study outcomes will be presented graphically also. Due to small sample sizes of subjects randomized to the Asia geographic region, this region will be pooled with the Eastern Europe region in the statistical analysis models.

7.4.2. Handling of Missing Data and Intercurrent Events (IE)

Intercurrent events in this study include the following:

- IE1: Premature discontinuation of study treatment
- IE2: Restricted/rescue medication use (criteria for restricted/rescue medication use is provided in Section 6.21)

The strategies to be used in the handling of intercurrent events and missing data for efficacy endpoints, when applicable, are provided below:

- Binary endpoints (primary and secondary efficacy endpoints):
 - IE1 and IE2: subject is considered a non-responder (composite strategy)
 - Missing data for Day 169: subject is considered a non-responder
- Continuous endpoints measured through time (SLEDAI-2K total score):
 - IE1 and IE2: data after IE1 and IE2 occurs will not be included in the analysis (hypothetical strategy)
 - Missing data caused by applying the intercurrent event handling described above and other missing data will be handled by the mixed effects models for repeated measures (MMRM) analysis
- Other efficacy endpoints:
 - Treatment policy strategy will be applied and all observed data during the treatment period will be used regardless of IE1 or IE2
 - Missing data for Day 169 for binary endpoints: subject is considered a non-responder for applicable endpoints

7.5. Analysis of Primary Efficacy Endpoints

7.5.1. Main Analysis

Response rates for subjects in the ALPN-101 group and in the placebo group will be calculated and the corresponding 95% CI will be reported for each treatment group. These response endpoints will be analyzed through Day 169 for subjects who complete treatment and through

the last assessment recorded ≤28 days after treatment discontinuation date for subjects who discontinue treatment early.

For the main analyses of SRI-4 response rate and BICLA response rate, non-responder imputation will be used for IE and missing data as described in Section 7.4.2.

Response rates will be compared using Cochran-Mantel-Haenszel (CMH) test statistic stratified by the factors used at randomization. Estimated treatment effect will be reported as the difference between the response rate in the ALPN-101 treatment group and the response rate in the placebo group. Corresponding 95% CI for the difference in proportions and the two-sided p-value for the difference will be reported.

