10.2. Sample Size

The primary purpose of this phase 2 study is to access the safety of ALPN-101 in subjects with moderate to severe SLE. As such, the anticipated sample size of approximately 130 subjects randomized 1:1 to receive ALPN-101 or placebo was not derived to support formal hypothesis testing of efficacy endpoints.

To estimate the power to detect potential differences in efficacy endpoints of primary interest, placebo response rates of 40% for SRI-4 and 20% for BILAG were assumed. A sample size of 65 subjects per treatment arm will provide 82% and 87% power to detect a difference of at least 25% between the ALPN-101 arm and the placebo arm at Day 169 in SRI-4 and BILAG response, respectively, based on a chi-square test with a two-sided significance level of 0.05 and no adjustments for multiple testing.

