Subjects who prematurely discontinue treatment with study drug should have all procedures outlined in the EOT visit and an unscheduled ECG performed as soon as possible, and not later than the next scheduled visit. To minimize missing data for efficacy and safety assessments, subjects who prematurely discontinue treatment, and who do not withdraw from the study, should otherwise continue their regular study visit schedule without receiving study drug. In subjects who are unable to continue their regularly scheduled visits, a follow-up phone call should occur approximately 8 weeks (corresponding to 5X half-life) after the last dose of study drug to determine the status of any ongoing AEs/ SAEs or the occurrence of any new AEs/SAEs.

Subjects who withdraw from the study prematurely (i.e., prior to Day 197), the End of Study (EOS) evaluations should be completed, if possible, preferably within 2 weeks of study drug discontinuation. In addition, a follow-up phone call should occur approximately 8 weeks (corresponding to 5x half-life) after the last dose of study drug to determine the status of any ongoing AEs/SAEs or the occurrence of any new AEs/SAEs.

It should be noted that while N=130 subjects were expected to be randomized in this study, enrollment was stopped at N=76 subjects.

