4.2. Determination of Sample Size

The primary purpose of this Phase 2 study is to assess the safety of ALPN-101 in subjects with moderate to severe SLE. As such, the anticipated sample size of 130 subjects randomized 1:1 to receive ALPN-101 or placebo was not derived to support formal hypothesis testing of efficacy endpoints.

Table 1 provides the estimated power to detect a range of potential differences in proportions. For these calculations, a sample size of 65 subjects per treatment group, a two-sided chi-square test statistic and a significance level (alpha) of 0.05 were used. Placebo response rates of 40% for SRI-4 and 20% for BICLA and effect sizes ranging from 15% to 35% were assumed.

No adjustments for multiplicity are planned for this early phase study.

SRI-4			BICLA		
Response Rate		Estimated	Response Rate		Estimated
Placebo	ALPN-101	Power*	Placebo	ALPN-101	Power*
40%	55%	40%	20%	35%	48%
40%	60%	63%	20%	40%	71%
40%	65%	82%	20%	45%	87%
40%	70%	94%	20%	50%	96%
40%	75%	99%	20%	55%	99%

Table 1: Estimated Power Based on N=65 Subjects per Treatment

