7.6.2. Analysis of Continuous Endpoints

MMRM will be used for the analysis of continuous longitudinal data. Terms in the model will include treatment group, baseline value of the analysis variable, stratification factors (concomitant oral immunosuppressive therapy use at enrollment and geographic region), analysis visit, and the interactions of treatment-by-visit and baseline value-by-visit as fixed effects. An unstructured covariance matrix will be used to model within-subject error. If the model fails to converge with an unstructured covariance matrix, a heterogeneous compound symmetric structure will be used. Kenward-Roger degrees of freedom, Type III sums of squares, and least squares (LS) mean values will be reported for each treatment group and for the difference between treatments. Standard errors and 95% CI for the estimated mean difference at each visit will be presented. Plots of LS mean values and 95% CIs by visit with separate lines for each treatment group will be provided for continuous secondary efficacy endpoints.

Annualized flare rates and cumulative prednisone-equivalent dose use will be analyzed using an analysis of variance model. Terms in the model include treatment group and stratification factors (concomitant oral immunosuppressive therapy use at enrollment and geographic region). Type III sums of squares, and least squares (LS) mean values will be reported for each treatment group and for the difference between treatments. Standard errors and 95% CI for the estimated mean difference will be presented.

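### The SRI-4 main analysis does not use baseline SLEDAI-2K: the analysis is valid, but it misses a cheap gain in precision in a trial stopped at 76 subjects

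*SAP*

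**What the plan says.** For both SRI-4 and BICLA, SAP 7.5.1 compares the response rates by a CMH test "stratified by the factors used at randomization". The effect reported is the difference between the two response rates with a 95% confidence interval. SAP 4.3 gives the two factors as background immunosuppressive therapy and geographic region. SAP 7.4.1 pools Asia with Eastern Europe in the analysis models, which leaves 2 x 2 = 4 strata.

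SLEDAI is scored on Day 1 before randomization (Protocol 6.2). SRI-4 requires, among other things, a fall of at least 4 points in SLEDAI-2K total score (SAP 6.5). BICLA is built on improvement in BILAG grades and requires only that SLEDAI-2K does not rise (SAP 6.6).

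For continuous longitudinal endpoints, which include change in SLEDAI-2K, the model contains the "baseline value of the analysis variable" (SAP 7.6.2). Otherwise baseline SLEDAI-2K (below 10, 10 or more) appears only in SAP 5.2, in a list of possible post hoc subgroups.

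The planned size was 130, but SAP 4.1 records that "enrollment was stopped at N=76 subjects". SAP 4.2 says that "the anticipated sample size of 130 subjects randomized 1:1 to receive ALPN-101 or placebo was not derived to support formal hypothesis testing" of efficacy endpoints.

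**The concern.** The chance of a 4-point fall should depend on where a subject starts. Inclusion Criterion 4 admits a Day 1 clinical score as low as 4. A subject with a total of 6 must lose 4/6 = 67% of it, and a subject at 14 must lose 4/14 = 29%. The SAP adjusts the change in this score for its baseline, but not the responder endpoint derived from the same score.

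Two things are at stake. The interval for the SRI-4 difference may be wider than it needs to be in a trial that enrolled 76 of 130. And a chance imbalance in baseline activity between two arms of about 38 goes uncorrected.

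**Working it through.** **Inputs from the documents.** Protocol 10.2: "A sample size of 65 subjects per treatment arm will provide 82% and 87% power to detect a difference of at least 25" percentage points, "based on a chi-square test with a two-sided significance level of 0.05 and no adjustments for multiple testing". SAP 4.2: "Placebo response rates of 40% for SRI-4 and 20% for BICLA and effect sizes ranging from 15% to 35% were assumed". Allocation is 1:1, and enrollment stopped at 76.

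**Assumptions.** 38 per arm, all 76 in the mITT population, planning rates unchanged, and a log-odds of response of 0 to 1.0 per SD of baseline SLEDAI-2K. Neither document gives this last figure.

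**1. The plan's power.** Power = Φ{[Δ − 1.96·√(2p̄(1−p̄)/n)] / √([p0(1−p0)+p1(1−p1)]/n)}.

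- SRI-4, 40% vs 65%, n = 65: (0.25 − 1.96 × 0.0876)/0.0848 = 0.923, so power is 82.2% (stated: 82%).
- BICLA, 20% vs 45%, n = 65: (0.25 − 1.96 × 0.0822)/0.0792 = 1.124, so power is 86.9% (stated: 87%).

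All ten cells of SAP Table 1 reproduce to within 1 point.

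**2. At 38 per arm, SRI-4.** (0.25 − 1.96 × 0.1146)/0.1109 = 0.229, so power is 59.1%. The 95% half-width is 1.96 × 0.1109 = 21.7 points. The loss of about 23 points of power comes from the smaller N, not from the choice of analysis.

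**3. Adding baseline SLEDAI-2K.** The adjusted estimate is RD = (1/N) Σ [expit(a + b + c′x_i) − expit(a + c′x_i)]. Here b is the treatment coefficient and x_i holds the stratification factors and baseline score. Trials of 76 subjects were simulated at 40% vs 65%. The half-width below is 21.7 × √(variance ratio), before any small-sample widening.

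| Assumed log-odds per SD | Variance ratio | 95% half-width (points) | Power gain over CMH, corrected test |
|---|---|---|---|
| 0 | 1.01-1.02 | 21.8-22.0 | 0-1 |
| 0.4 | 0.99 | 21.6 | about 1 |
| 0.7 | 0.90 | 20.6 | about 3 |
| 1.0 | 0.85 | 20.0 | about 7 |

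A separate simulation (4,000 trials per setting, four strata, baseline mean 10 and SD 3) agrees. Its variance ratios were 1.02, 0.985, 0.922 and 0.848 at odds ratios of 1, 1.5, 2 and 3 per SD.

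**4. Size and coverage.** The uncorrected robust interval is too short at this sample size. Coverage was about 93-94% and type I error 6.4-7.0%. A small-sample correction restores coverage to about 94-95%, with type I error of 5.2-5.9%. The power gains in the table use the corrected test and are still slightly generous for that reason.

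**5. Chance imbalance.** The SD of the between-arm difference in mean baseline is √(2/38) = 0.23 SD. An imbalance of that size or more occurs in about a third of trials. It would shift the expected crude difference from 25 points to 22.9 or 27.1 (log-odds 0.4), 21.6 or 28.4 (0.7), or 20.5 or 29.4 (1.0).

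**6. SLEDAI-2K as a third CMH stratum.** Splitting at 10 changed simulated SRI-4 power from 59.4% to 57.1% (odds ratio 1), 59.4% to 57.3% (1.5), 61.4% to 60.9% (2) and 58.9% to 61.9% (3). It costs power unless the association is strong.

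**The case against.** The strongest reply is that nothing is wrong. Stratified CMH is valid and follows the randomization, efficacy is a secondary objective, and the sample size was not derived for formal efficacy testing. That stands, and it makes this an efficiency point.

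A reader might go further than the documents allow in four ways.

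- **That baseline SLEDAI-2K is known to be strongly prognostic.** No section gives the association. The percentage argument is also softer than it looks. Items are scored present or absent with fixed weights (SAP 15.3.1), and arthritis alone carries 4 points, so subjects at 6 and at 14 can both qualify by clearing one item. Rescue medication and treatment discontinuation count as non-response (SAP 7.4.2). If more active disease leads to more rescue, that pulls the other way. A link is plausible from the definition, but its strength is unknown.
- **That the same argument covers BICLA.** It does not, because BICLA is not a points-reduction response in SLEDAI-2K.
- **That all of the simulated power gain is real.** With an uncorrected robust standard error, part of it is an inflated type I error.
- **That the SAP contains no adjusted analysis anywhere.** The contents list a section 7.5.2.1 on robustness to the missing-data method, and that section is not in the public text. A supplementary adjusted analysis cannot be excluded. The point concerns the main analysis in 7.5.1.

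**Conclusion.** The point holds for SRI-4 as a missed efficiency. The main analysis uses no measure of baseline disease activity, although one is collected before dosing and the endpoint is defined as a fall from it. The gain is nil or a slight loss if baseline SLEDAI-2K is not prognostic, negligible at a log-odds of 0.4 per SD, and useful at 0.7 to 1.0: variance down 10-15% and about 3 to 7 points of power. Even the upper end recovers less than a third of the roughly 23 points lost by stopping at 76 (7/23 = 30%). These figures rest on the assumptions listed above, and the true arm split and mITT size are not given. The documents do not support calling the planned CMH analysis biased or invalid.

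**What to change.** In an SAP amendment before unblinding, add for SRI-4 a standardised (g-computation) risk difference. Take it from a logistic model with treatment, background therapy, region (Asia pooled with Eastern Europe, as in SAP 7.4.1) and continuous baseline SLEDAI-2K. Specify a small-sample-corrected or bootstrap 95% interval, not the plain robust one. Report the estimate with its own p-value beside the CMH result. If only the CMH p-value were kept, the estimate and interval would improve but the reported test would not. State in advance which of the two results is the main one.

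Do not add SLEDAI-2K as a further CMH stratum. If BICLA is to be adjusted, baseline BILAG activity is the natural covariate.

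The cost is a few lines of SAP text and code, with no new data. The downsides are a second, model-based result that can disagree with the CMH p-value, and a 1-2% loss in variance if baseline SLEDAI-2K turns out not to be prognostic.
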